8.3.7 Trial-limiting Toxicity

Trial-limiting toxicity (TOX) is defined as the occurrence of any adverse event leading to treatment discontinuation that is possibly, probably, or definitely related to nivolumab, ipilimumab, or ipilimumab in combination with nivolumab during the initial 12 weeks of treatment, unless there is a clear alternative explanation. Additional discontinuation criteria regarding the advanced prostate cohorts can be found in [Section 6.6.1.4](#).

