9.3 INTERIM ANALYSES

9.3.1 Safety and Futility Monitoring

Ongoing monitoring for safety and futility will be implemented based on the method of Thall and colleagues (Thall et al, 1995) separately in the CD8 high and CD8 low tumor groups for advanced metastatic cancer and advanced prostate cancer participants. Monitoring will be ongoing during enrollment in each group, once a participant receives treatment and their first treatment biopsy is performed. Screening and accrual to each group will continue until sufficient

information is available to assess the stopping rules as defined below. Stopping rules and operating characteristics were calculated using Multic Lean v2.1.

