9.3.1.1 Safety Monitoring

For trial monitoring and decisions about future trials, TOX criteria are defined in [Section 8.3.7](#). A participant who voluntarily leaves the trial for any reason, including toxicity that does not meet the TOX criteria, will not count as having a TOX. Denote the probability of TOX by θ_T . The stopping rule for advanced metastatic cancer arms is given by the following probability statement: $\Pr(\theta_T > 0.40 \mid \text{data}) > 0.975$. That is, the trial will be stopped if, at any time during the study, it is determined that there is > 97.5% chance that the TOX rate is > 40%. The stopping rules assume a constant TOX rate for “standard therapy” of 0.40 ([Larkin et al, 2015](#); [Wolchok et al, 2017](#)) and a prior $\theta_T \sim \text{beta}(0.8, 1.2)$ for the current study. The stopping boundaries for this toxicity rule are to terminate the trial if the number of participants with TOX compared to the number of participants having received treatment exceeds the limits in [Table 14](#).

Table 14: Rules for Safety and Futility Monitoring per Arm

If there are this many (or more) participants evaluable for response	Stop the arm if there are this many (or more) participants with a TOX event:	Stop the arm if there are this many (or fewer) participants who meet the definition of success defined above:
20	13	1
40	23	3
60	32	6
80	41	9
100	50	12
120	59	15
140	68	19

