9.3.1.2 Futility Monitoring

For trial monitoring, “success” will be defined separately by tumor group. For participants with CD8 low tumors, participants will be counted as having success if they meet the definition of CBR *or* if the tumor converts from CD8 low to CD8 high expression. For participants in the CD8 high tumor group, participants will be counted as success if they meet the definition of CBR. Denote the probability of success by θ_s . We assume $\theta_s \sim \text{beta}(0.4, 1.6)$. The stopping rule is given by the following probability statement: $\Pr(\theta_s < 0.20 \mid \text{data}) > 0.975$. That is, participant enrollment for advanced metastatic cancer arms will be stopped if, at any analysis time, it is determined that there is > 97.5% chance that the CBR is < 20%, a constant rate that is at the average expected response rate for these participants. The stopping boundaries for this futility

rule, shown in [Table 14](#), are designed to terminate enrollment on the arm if the number of overall responses compared with the number of participants enrolled who are evaluable does not meet the requirements of this table. A participant is evaluable for benefit either on the date of disease assessment or the date the participant goes off study without benefit or if the participant does not receive the scheduled disease assessment within 3 weeks without associated scheduling delay. Monitoring will be carried out during enrollment in each advanced metastatic cancer arm. Participants who withdraw from the study after receiving treatment but before undergoing on-treatment biopsies or who miss the evaluation window without associated treatment delay will be counted as not benefitting and therefore evaluable for analysis. CBR is defined as best response of CR or partial response (PR) any time or stable disease (SD) lasting 6 months. For futility monitoring purposes, confirmation of response (CR or PR) is not required. Additionally, a participant who has been on study between 12 weeks and 6 months and has SD at the time of data collection will be counted as a success for that futility analysis. If that participant later progresses and no longer meets the SD definition, their updated information will be included in the monitoring analysis ([Table 14](#)).

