9.3.1.3 Joint Operating Characteristics for Safety and Futility Monitoring

The rules above will apply independently to each CD8 high or CD8 advanced metastatic cancer arm. It is estimated that there will be 40 participants with CD8 high tumors and 160 participants with CD8 low tumors in presenting the operating characteristics below. The probability of stopping at 20 participants provides the probability of stopping early in the CD8 high tumor group, assuming only 40 participants are entered. [Table 15](#) shows the operating characteristics under varying toxicity and response rates.

Table 15: Operating Characteristics Under Varying Toxicity and Response Rates

True Overall Toxicity Rate	True Overall Response Rate	Probability of Stopping at 20 Participants	Probability of Stopping Before 160 Participants	Median (25 th %ile, 75 th %ile) for “Cold” Cohort
0.10	0.05	0.74	>0.99	20 (20, 40)
	0.10	0.39	0.96	40 (20, 80)
	0.20	0.07	0.12	160 (160, 160)
	0.30	0.01	0.01	160 (160, 160)
	0.40	0.001	0.001	160 (160, 160)
0.20	0.05	0.74	>0.99	20 (20, 40)
	0.10	0.39	0.96	40 (20, 80)
	0.20	0.07	0.12	160 (160, 160)
	0.30	0.01	0.01	160 (160, 160)

True Overall Toxicity Rate	True Overall Response Rate	Probability of Stopping at 20 Participants	Probability of Stopping Before 160 Participants	Median (25 th %ile, 75 th %ile) for “Cold” Cohort
	0.40	0.001	0.001	160 (160, 160)
0.30	0.05	0.74	>0.99	20 (20, 40)
	0.10	0.39	0.96	40 (20, 80)
	0.20	0.07	0.12	160 (160, 160)
	0.30	0.01	0.01	160 (160, 160)
	0.40	0.002	0.002	160 (160, 160)
0.40	0.05	0.74	>0.99	20 (20, 40)
	0.10	0.40	0.96	40 (20, 80)
	0.20	0.09	0.19	160 (160, 160)
	0.30	0.03	0.09	160 (160, 160)
	0.40	0.02	0.08	160 (160, 160)
0.50	0.05	0.77	>0.99	20 (20, 20)
	0.10	0.47	0.99	40 (20, 60)
	0.20	0.19	0.78	80 (40, 140)
	0.30	0.14	0.75	80 (40, 140)
	0.40	0.13	0.75	80 (40, 160)

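### In the metastatic arms the TOX stopping rule has two conflicting denominators, neither of them the completed 12-week window that Tables 14 and 15 assume

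*Protocol*

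**What the plan says.** Protocol 9.3.1.1 stops an advanced metastatic arm when "there is > 97.5% chance that the TOX rate is > 40"%, under a beta(0.8, 1.2) prior. The rule is said to hold at any time. The operational sentence stops when "the number of participants with TOX compared to the number of participants having received treatment exceeds the limits" in Table 14.

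The size column of Table 14 uses another count: "If there are this many (or more) participants evaluable for response". Evaluability is defined in 9.3.1.2, and only for benefit: "A participant is evaluable for benefit either on the date of disease assessment or the date the participant goes off study without benefit", or on missing the scheduled assessment. The first disease assessment in the metastatic arms is at Cycle 4 Day 1 (Tables 1 and 2 of the Schedule of Activities), about week 9 on three-week cycles.

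A TOX is a related adverse event leading to discontinuation "during the initial 12 weeks of treatment, unless there is a clear alternative explanation" (8.3.7). On accrual, 9.3.1 says "Screening and accrual to each group will continue until sufficient" information exists to assess the rules. It describes no pause for TOX data to mature.

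Table 15 then gives "operating characteristics under varying toxicity and response rates". At toxicity 0.50 and response 0.40 it shows 0.13 at 20 participants and 0.75 before 160. Section 9.3.1.3 uses the 20-participant figure as the early-stop probability for the CD8-high arm, expected to reach 40. SAP 5.9 defines no denominator and refers back to protocol 9.3.

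**The concern.** Under the operational sentence, a participant dosed the day before a look adds one to the denominator and almost nothing to the chance of an event. The error runs one way, against stopping, and is largest at the first look, when the share of participants still in the window is highest. The table header largely avoids this but contradicts the sentence that points to it, and its count still opens about three weeks before the TOX window closes.

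Two teams applying the same section could therefore reach different stopping decisions from the same data, and on one reading the protection tabulated in Table 15 is not delivered. The synopsis says there is no independent data safety monitoring committee, so for the metastatic arms this numeric rule carries real weight.

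**Working it through.** **1. Reproduce Table 14.** The limit at n is the smallest k with Pr(θ > 0.40 | beta(0.8 + k, 1.2 + n − k)) > 0.975. At n = 20, k = 13 gives 0.985 and k = 12 gives 0.957, so the limit is 13. The same formula returns all seven limits: 13, 23, 32, 41, 50, 59, 68.

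**2. Reproduce Table 15 (toxicity 0.50).** With all 20 outcomes known, Pr(X ≥ 13) for X ~ Bin(20, 0.5) is 137,980 / 1,048,576 = 0.132, matching 0.13. An exact recursion over looks at 20, 40, ..., 140 gives cumulative stopping of 0.132, 0.257, 0.404, 0.525, 0.620, 0.693, 0.751, matching 0.75. So Table 15 assumes complete TOX data at every look and looks every 20.

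**3. Why the treated count differs.** Take 5 per month (4.345 / 5 = 0.869 weeks apart, evenly spaced), onset uniform over 12 weeks, and a look as the 20th participant is dosed. The participant dosed j places earlier has been observed for min(1, 0.869j/12) of the window. For j = 0 to 13 these fractions sum to 91 × 0.0724 = 6.6, and j = 14 to 19 add 6, giving 12.6 windows out of 20. Expected TOX events at a 50% rate are 0.5 × 12.6 = 6.3 rather than 10, against an unchanged limit of 13.

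**4. Size at true TOX 50%.** The documents give neither accrual rate nor onset timing, so both are assumed. For scale, 160 CD8-low participants over 2 to 4 years is 160/24 = 6.7 to 160/48 = 3.3 per month, and 40 CD8-high is 1.7 to 0.8 per month. Simulation uses Poisson accrual, the TOX rule only, 6,000 trials per cell and looks every 20. Each cell shows uniform onset / early-weighted onset (12 × beta(1,2) weeks).

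| Accrual per month | Treated: stop at 20 | Treated: before 160 | Evaluable (week 9): stop at 20 | Evaluable: before 160 |
|---|---|---|---|---|
| 0.5 | 0.06 / 0.07 | 0.70 / 0.70 | 0.12 / 0.12 | 0.74 / 0.75 |
| 1 | 0.05 / 0.06 | 0.66 / 0.69 | 0.12 / 0.13 | 0.74 / 0.75 |
| 2 | 0.02 / 0.03 | 0.62 / 0.65 | 0.11 / 0.13 | 0.74 / 0.75 |
| 4 | 0.01 / 0.01 | 0.53 / 0.60 | 0.11 / 0.13 | 0.73 / 0.75 |
| 8 | 0.00 / 0.00 | 0.34 / 0.47 | 0.09 / 0.13 | 0.71 / 0.75 |
| Table 15 | 0.13 | 0.75 | 0.13 | 0.75 |

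At 10 per month the treated count gives about 0.25 (uniform) or 0.39 (early-weighted) before 160.

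**5. True TOX 60%.** Over 0.5 to 8 per month, the treated count stops at 20 with probability 0.00 to 0.27 instead of 0.42. It still stops before 160 in 0.96 to 0.998 of trials, against 0.999.

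**6. Completed windows.** Counting only completed 12-week windows returns 0.132 and 0.751. Because accrual continues meanwhile, the median enrolled at a stop is about 87 to 105 at 2 to 8 per month, against 80 in Table 15.

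**The case against.** A reader might infer that the rule simply divides by everyone treated, so that it fires late. The documents do not settle that. Three points count against the stronger reading.

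- **The table header.** Under the evaluable count the shortfall before 160 is at most about 4 points. Nearly all of the loss depends on which of the two conflicting texts is followed.
- **The look schedule.** The text says the rule holds at any time. With the treated count and the posterior rechecked at every TOX event, stopping before 160 at TOX 50% is 0.78, 0.72 and 0.54 at 2, 4 and 8 per month, so against 0.75 the loss is nil at slow accrual. But Table 15 was computed with looks every 20. Rechecking complete data continuously would exceed 0.75, so this comparison flatters the treated count.
- **The words (or more) in Table 14.** Read literally, the limit of 13 stays in force from 20 to 39 participants. Checked at every event, that stops early: 0.96 to 0.996 at TOX 50%, and 0.45 to 0.81 at TOX 40%, where Table 15 implies about 0.08. Late firing is therefore not the only possible failure.

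A reader might also take this for the trial's only formal safety stop. That holds for the metastatic arms only: protocol 6.6.1.4 gives the prostate cohorts a safety pause, a 4-of-5 rule and an 8-event enrolment suspension. Sponsor review of serious events continues throughout.

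Finally, the accrual sentence in 9.3.1 ties accrual to having sufficient information to assess the rules. That shows awareness of the issue but does not say what makes a participant's TOX status mature. What stands is the contradiction, and that neither count matches the tables.

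**Conclusion.** The point holds for the advanced metastatic arms as a defect of definition. The reproduction of Tables 14 and 15 is exact and needs no assumption: the tables describe complete 12-week TOX data, and neither stated denominator supplies it.

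The size is conditional on assumed accrual and onset. With the treated count, looks every 20 and uniform onset, the 0.75 in Table 15 becomes about 0.62 to 0.25 at 2 to 10 per month, and the 0.13 at the first look becomes 0.02 or less. The CD8-high arm would probably accrue more slowly, but its quoted early-stop probability rests on that first look, which still falls to about 0.02 to 0.06 at 1 to 2 per month. At a 60% TOX rate the harm is mainly delay. With the evaluable count the loss is small, and with continuous checking it may vanish. The text should be corrected because it does not say which of these cases applies.

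**What to change.** In the 9.3.1.1 sentence, the Table 14 header for the TOX column and SAP 5.9:

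- Define the TOX denominator as participants who have completed the 12-week window of 8.3.7 or had a TOX within it, taken in order of enrolment. The ordering matters: if events enter at once while event-free participants wait 12 weeks, the count is enriched for events and the rule over-stops.
- State that the limits apply at the listed sizes (20, 40, ..., 140), and what (or more) means between them.
- State that Table 15 assumes complete 12-week TOX data and that accrual continues meanwhile, so more participants will be enrolled at a stop than its median shows.

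This restores 0.13 and 0.75 and leaves the integer limits unchanged. The cost is wording and minor monitoring code, plus a delay: each look comes up to 12 weeks after the nth participant is dosed, during which rate × 12 / 4.345 further participants enter (5.5, 11 and 22 at 2, 4 and 8 per month).

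Crediting participants still in the window with weeks observed / 12 would shorten that delay, but it is optional. It gives 0.62 to 0.76 at TOX 50% with false stops of 0.04 to 0.11 at TOX 40%, relies on roughly uniform onset, and gives up the integer limits.

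### Table 14's TOX limits satisfy the protocol's probability rule only at exactly 20, 40, ..., 140 participants, but the table applies them to that number 'or more' and counts participants evaluable for response where the text counts participants treated.

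*Protocol*

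**What the plan says.** Protocol 9.3.1.1 gives the safety rule for the advanced metastatic cancer arms in words. The condition for stopping is that "it is determined that there is > 97.5% chance that the TOX rate is > 40" per cent. It is not confined to scheduled looks: "the trial will be stopped if, at any time during the study". The prior for the TOX rate is beta(0.8, 1.2). The working instruction, "terminate the trial if the number of participants with TOX compared to the number of participants having received treatment exceeds the limits in", then names Table 14 as the source of the limits.

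That table has a single index column for both the TOX and the futility limits. It is headed "If there are this many (or more) participants evaluable for response" and lists 20, 40, ..., 140. The TOX column is headed "Stop the arm if there are this many (or more) participants with a TOX event" and lists 13, 23, 32, 41, 50, 59 and 68. No limits are given between multiples of 20.

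Protocol 9.3.1.2 makes a participant evaluable at a disease assessment, on going off study without benefit, or on missing an assessment. Protocol 8.3.7 counts TOX over the first 12 weeks of treatment. SAP 5.9 refers back to protocol 9.3 and does not settle which count applies.

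**The concern.** The text and the table state different rules, in two respects.

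First, a limit derived for exactly 20 participants is carried forward to 21, 22 and so on up to 39. The same number of TOX events among more participants is weaker evidence of excess toxicity, so the table can call for a stop when the stated probability is far below 0.975.

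Second, the text divides by participants treated and the table by participants evaluable for response. TOX counts from the first dose, while the first scheduled disease assessment in the metastatic arms is Cycle 4 Day 1, about 3 × 3 = 9 weeks in. During accrual the number treated will normally exceed the number evaluable.

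At stake is whether an arm with an acceptable TOX rate is closed by a table that contradicts its own rule, and whether Table 15 describes the rule that would be used. The protocol has no independent monitoring committee to settle the reading.

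**Working it through.** **Inputs.** Prior beta(0.8, 1.2), reference rate 0.40, threshold 0.975 and the Table 14 limits (protocol 9.3.1.1); planning arm sizes of 40 and 160 and the Table 15 stopping probabilities (protocol 9.3.1.3).

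**Formula.** With x TOX events among n participants, the posterior is beta(0.8 + x, 1.2 + n − x). The rule stops at the smallest x for which Pr(rate > 0.40) exceeds 0.975.

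**Reproducing the plan.** At n = 20, 40, 60, 80, 100, 120 and 140 this gives 13, 23, 32, 41, 50, 59 and 68, matching all seven rows. At n = 20, for example, 13 events give 0.985 and 12 give 0.957. With looks only at those sizes, all 25 rows of Table 15 are reproduced within 2 percentage points. For true toxicity 0.40 and response 0.40, the computed probabilities of stopping at 20 and before 160 are 0.0215 and 0.079; the table prints 0.02 and 0.08.

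**Effect of 'or more' in the first row.** The row for 20 keeps the limit at 13 until 40 is reached:

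| n | Posterior with 13 TOX | TOX needed under the stated rule |
|---|---|---|
| 20 | 0.985 | 13 |
| 21 | 0.974 | 14 |
| 25 | 0.877 | 16 |
| 30 | 0.633 | 18 |
| 35 | 0.358 | 20 |
| 39 | 0.193 | 22 |

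Later rows fail in the same way, though less severely. At the last n each row covers, the posterior is 0.430 for 23/59, 0.530 for 32/79, 0.607 for 41/99, 0.668 for 50/119, 0.717 for 59/139 and 0.757 for 68/159.

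**Effect on the chance of a safety stop.** These are exact binomial calculations for the TOX rule alone. They treat each TOX outcome as known at once, so they involve no accrual assumption. 'As worded' uses the latest row reached and checks it after every participant.

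| True TOX rate | By n | As worded | Looks at exact sizes | Stated rule at every n from 20 |
|---|---|---|---|---|
| 0.20 | 40 | 0.036 | < 0.001 | < 0.001 |
| 0.30 | 40 | 0.38 | 0.0015 | 0.003 |
| 0.40 | 40 | 0.84 | 0.033 | 0.061 |
| 0.40 | 160 | 0.87 | 0.079 | 0.127 |

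**Treated against evaluable.** Suppose 20 are evaluable and 13 have had TOX. If 25, 30, 35 or 40 have been treated, the posterior based on participants treated is 0.877, 0.633, 0.358 or 0.162. These excesses of 5 to 20 are assumptions, because no accrual rate is given. The mismatch can also delay a stop: 13 TOX among 20 treated meets the stated rule (0.985), but no table row applies while fewer than 20 are evaluable.

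**The case against.** The best defence is that the rows are plainly interim looks. Table 15 is reproduced on that reading. The probability statement governs, and the table only tabulates it. Moreover, if 'or more' were taken without limit, the row for 20 would still apply at 140 and the later TOX rows would be redundant, so that cannot be intended. This is a good argument about intent, and it confirms that the limits are not miscalculated. It does not remove the conflict: the header says 'or more', the text says the rule operates at any time, and neither says that the rows hold only at those sizes. The 'as worded' figures above already use the milder reading, in which each row lapses when the next is reached.

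It is also fair that 'or more' does no harm in the futility column, where the same few successes among more participants is stronger evidence of futility. Treated need not always exceed evaluable either: participants who go off study without benefit become evaluable that day, and the two counts converge once accrual ends.

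Two stronger readings are tempting but not supported.

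- Protocol 9.3.1 and SAP 5.9 say monitoring runs "once a participant receives treatment and their first treatment biopsy is performed". A reader might infer a further denominator that leaves out TOX occurring before the biopsy. The sentence describes when monitoring runs and excludes nobody. Protocol 9.3.1.2 counts as evaluable those who withdraw before an on-treatment biopsy, and protocol 4.1 requires such biopsies only where medically feasible.
- A reader might estimate the effect of the lag by giving everyone treated the full 12-week TOX risk. That overstates it, since the participants not yet evaluable have been followed for only part of the window.

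**Conclusion.** The point holds. The TOX limits are right at exactly 20, 40, ..., 140 and wrong at the sizes between, apart from 41, where 23 events still meet the rule (posterior 0.979). The table's index also contradicts the text's denominator.

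At a true TOX rate of 0.40, applying the row in force continuously gives a safety-stop probability of 0.84 by 40 participants and 0.87 before 160, against 0.033 and 0.079 at exact looks. At a true rate of 0.30 it is 0.38 by 40, against 0.0015. These results follow from 'or more' alone, assuming independent TOX outcomes known at once and a check after each participant. The treated/evaluable mismatch adds to them, or delays a stop, by an amount the documents do not allow one to fix.

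It would go too far to infer that the calibration or Table 15 is in error, or that any arm was in fact stopped wrongly. Table 15 is correct for looks at exact sizes; what conflicts with it is the rule that Table 14 prints.

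**What to change.** 1. Give the TOX and success limits separate index columns, with success indexed by participants evaluable for response.
2. Use one TOX denominator in both text and table, with the same follow-up requirement for participants with and without TOX. One example is the first n treated, assessed when all n have completed the 12-week window or left treatment. TOX cases must not enter earlier than non-TOX cases: counting each participant on having a TOX or on completing 12 weeks biases the rate upward. In a simulation at a true rate of 0.40, with looks every 20, even accrual of 1 to 1.5 per week and TOX uniform over 12 weeks (all assumed except the look sizes), that denominator raised the stop probability from about 0.08 to between 0.16 and 0.22.
3. For the TOX column, choose one of two forms. Either delete 'or more' from the index and state that the rows are looks at exactly 20, 40, ..., 140, as Table 15 assumes, amending 'at any time' to match. Or print the limit for every n from the stated rule and recompute Table 15; the stop probability at a true rate of 0.40 is then about 0.13 before 160 with monitoring at every n from 20.
4. Align the text, which stops when the count "compared to the number of participants having received treatment exceeds the limits", with the table's 'this many or more'. The posterior at each limit supports the table.
5. Have SAP 5.9 point to the reconciled rule.

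The cost is a revised table and a few sentences, with no new data. If every n is monitored, the operating characteristics become slightly less favourable.
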